#### 11.8.2.6 Migraine and Headache Diary

Migraine and headache diary details will be listed by subject. Menstrual cycle details will also be listed by subject.

In DDP: Listing 16.2.6.1, Listing 16.2.6.2 and Listing 16.2.6.5

### 11.8.3 Exploratory Analysis

#### 11.8.3.1 Sustained Pain-free at 24 Hours

Number and percentage of subjects who are “sustained pain-free” at 24 hours (as defined in section 10.15.1) will be summarised treatment overall. The paired difference in number of subjects sustained pain-free (LAT8881 – Placebo) will be calculated as mentioned in section 10.16.

The summary will be based on Per-Protocol population.

In DDP: Table 14.2.5

#### 11.8.3.2 Time to First Pain-free Timepoint

The number and percentage of subjects with their first pain free timepoint will be presented by timepoint. The paired difference in the number of subjects with their first pain free timepoint will be calculated as mentioned in section 10.16.

Time taken to first pain-free timepoint will also be analysed using Kaplan-Meier curve. Time to first pain-free timepoint will be calculated based on the actual time taken from IMP as mentioned in section 10.15.5.

In DDP: Table 14.2.6.1, Figure 14.2.6.2

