4.2 Secondary objectives

1. To evaluate the effect of oral LAT8881 on migraine-associated symptoms compared with placebo, when assessed by the change in symptoms based on a 11- point Likert scale
2. To investigate the percentage of subjects achieving “no headache pain” following treatment with oral LAT8881 compared with placebo at any timepoint to 8 hours post dose, with no use of rescue medication
3. To evaluate the safety and tolerability of single doses of oral LAT8881 in subjects with migraine headache

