14.5 Analysis of efficacy data

The primary population for analysis of efficacy data is the PP population. All summary tables and results of statistical analyses will be presented for the PP population for all efficacy endpoints. In addition, all

summary tables and results will be presented for the FAS population.

Individual pain score-time profiles for each treatment within each subject will be presented graphically. The difference between the NRS pain scores at each timepoint for LAT8881 60 mg compared with placebo within each subject will be estimated and presented graphically. The number of subjects, mean, standard deviation, minimum and maximum NRS pain score at each timepoint, change from baseline, difference between treatments at each timepoint and change from baseline difference between treatments will be presented for each treatment overall and within each treatment period.

Nausea, photophobia and phonophobia symptom scores will be summarised and presented in the same way as the pain scores. The number and percent of headaches with each most troublesome symptom of migraine including nausea, cognitive impairment, dizziness, functional disability, photophobia and phonophobia will be summarised for each treatment. The most troublesome symptom scores will be summarised and presented in the same way as the pain scores.

The number and percent of subjects with 'no headache pain' at each time point will be presented for each treatment. Two-way tables will present the presence/absence of pain classified for each treatment at each timepoint. Absence of pain will be defined as a pain NRS score of 0 or 1.

The number and percent of subjects who are "sustained pain-free" at 24 hours after dose of IMP will be presented by treatment. A two-way table will present the "sustained pain-free" status for subjects on each treatment.

The number and percent of subjects will be summarised by their first pain-free timepoint. A two-way table will present the classification of each subject's first pain-free timepoint by treatment. Kaplan-Meier curves will present the time to first pain-free timepoint.

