### 10.15.4 Responder

Subjects achieving no migraine headache pain at each time point in each study period will be separately flagged for analysis. Presence or absence of pain will be determined as follows:

- Absence: NRS Pain score 0 or 1 at the corresponding timepoint.
- Presence: NRS Pain score more than 1 at the corresponding timepoint.

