### 10.15.5 Time to First Pain-Free Timepoint

For NRS scores for pain, subjects achieving no migraine headache pain timepoints will be flagged for each subject within each study period. The first pain-free timepoint in which the no migraine (score 0 or 1) achieved will be considered as the time to first pain-free timepoint. Time to first pain-free timepoint will be calculated based on the actual time difference as below.

Time (hours) = (Time the corresponding timepoint recorded - Time IMP was taken) / 60.

Subjects who did not achieve no migraine at 24 hours will be censored at 24 hours.

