## 10.16 Paired Difference in Pain-Free Subjects

Difference between treatments (LAT8881 – Placebo) for No Headache Pain at each timepoint, Sustained Pain-Free at 24 hours and First Pain-Free Timepoint will be calculated as below for the percentage difference; the numerator represents the difference in the number of subjects.

	Placebo		Total
	Pain free	Pain	
LAT8881			
Pain free	a	b	a + b
Pain	c	d	c + d

Total	a + c	B + d	a + b + c + d
-------	-------	-------	---------------

$$\text{Pain free for placebo (\%)} = \frac{a + c}{a + b + c + d}$$

$$\text{Pain free for LAT8881 (\%)} = \frac{a + b}{a + b + c + d}$$

$$\text{Pain free (LAT8881 - Placebo) (\%)} = \frac{a + b}{a + c + b + d} - \frac{a + c}{a + b + c + d} = \frac{b - c}{a + b + c + d}$$

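### Filled with first-at-t counts, SAP 10.16's two-level table groups subjects already pain-free with those still in pain, so the paired difference for first pain-free timepoint has no fixed direction

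*SAP*

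**What the plan says.** SAP 11.8.3.2 plans three outputs for this endpoint: counts, a paired difference and a Kaplan-Meier curve. On the counts: "The number and percentage of subjects with their first pain free timepoint will be presented by timepoint". On the paired difference: "The paired difference in the number of subjects with their first pain free timepoint will be calculated as mentioned in section 10.16".

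SAP 10.16 uses a single 2×2 table for three endpoints. Besides no headache pain at each timepoint, it says that "Sustained Pain-Free at 24 hours and First Pain-Free Timepoint will be calculated as below for the percentage difference", and that "the numerator represents the difference in the number of subjects". The rows (LAT8881) and columns (placebo) have two levels only, 'Pain free' and 'Pain'.

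Two definitions bear on the cells. SAP 10.15.5: "The first pain-free timepoint in which the no migraine (score 0 or 1) achieved will be considered as the time to first pain-free timepoint". SAP 10.15.4, written for the responder flag: "Presence: NRS Pain score more than 1 at the corresponding timepoint". Neither says where a subject goes at time t if he or she was already pain-free before t.

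Protocol 14.5 planned a different paired display, a two-way table classifying each subject's "first pain-free timepoint by treatment", together with Kaplan-Meier curves. SAP 8.1, which lists changes to the planned analyses, does not mention replacing that table.

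**The concern.** A subject has at most one first pain-free timepoint per period. Someone pain-free from 1 hour is therefore not first pain-free at 4 hours, and in a table with two levels the only place left is 'Pain'. That cell then mixes subjects whose headache has resolved with subjects whose headache has not.

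The result has no consistent meaning as better or worse. First relief at 24 hours scores the same as first relief at 0.5 hours, and a treatment can score negatively at a late time because its responders were counted earlier.

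This table is the planned within-subject comparison for the endpoint, and Protocol 14.1 asks that comparisons respect the pairing where feasible. Its sign at late timepoints could disagree with the Kaplan-Meier curve reported beside it.

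**Working it through.** **Inputs.** The seven post-dose times (SAP 10.3), the 10.16 formula, and n = 20 planned completers (SAP 4.2). The documents give no pain-free rates, so every rate below is an assumption. Rescue use is taken as nil in the examples.

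**The plan's own formula.** With n = a + b + c + d, (a + b)/n − (a + c)/n = (b − c)/n. The identity is exact; the difficulty lies in what the cells contain.

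**What the difference measures.** Let C(t) be the LAT8881 minus placebo difference in the proportion pain-free at or before t, and F(t) the difference in the proportion first pain-free at t. Then F(t) = C(t) − C(previous t), and the F(t) sum to C(24). So F(t) is negative whenever the gap narrows, even if LAT8881 is still ahead. If the 24-hour totals are equal and LAT8881 led at any time, at least one later F(t) must be negative.

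**Example 1: faster drug, same 24-hour total (16/20 on each; every responder one timepoint earlier on LAT8881).**

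| Hours | 0.5 | 1 | 1.5 | 2 | 4 | 8 | 24 |
|---|---|---|---|---|---|---|---|
| LAT8881, first at t | 1 | 2 | 3 | 4 | 4 | 2 | 0 |
| Placebo, first at t | 0 | 1 | 2 | 3 | 4 | 4 | 2 |
| F(t), points | +5 | +5 | +5 | +5 | 0 | −10 | −10 |
| C(t), points | +5 | +10 | +15 | +20 | +20 | +10 | 0 |

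At 8 hours the LAT8881 'Pain' row holds 20 − 2 = 18 subjects. Of these, 1 + 2 + 3 + 4 + 4 = 14 became pain-free earlier and 4 never did. At 24 hours all 16 responders sit in that row.

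**Example 2: faster drug that also raises the total (15/20 against 8/20).** First-at-t counts are 1, 2, 2, 2, 3, 3, 2 on LAT8881 and 0, 1, 1, 1, 2, 2, 1 on placebo. F(t) is +5 points at all seven times, and C(t) rises from +5 to +35. Nothing turns negative.

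**Example 3: assumed curves.** Cumulative pain-free is 5, 15, 25, 35, 55, 70, 85% on LAT8881 and 2, 6, 10, 15, 35, 55, 80% on placebo. Differencing each curve gives first-at-t values of 5, 10, 10, 10, 20, 15, 15 and 2, 4, 4, 5, 20, 20, 25. F(t) is +3, +6, +6, +5, 0, −5, −10. C(t) is +3, +9, +15, +20, +20, +15, +5.

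**Range.** Base chances of first relief in the seven intervals were set at 3, 6, 8, 12, 25, 30 and 40% among those not yet pain-free. Placebo used 1 − (1 − base)^k with k = 0.25, 0.5, 1 and 1.5, and LAT8881 raised the placebo term (1 − hazard) to the power HR. Expected differences in points:

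| Placebo by 24 h | HR | LAT8881 by 24 h | F(8) | F(24) | C(24) |
|---|---|---|---|---|---|
| 31% | 2 | 52% | +4.8 | +4.6 | +21.2 |
| 52% | 2 | 77% | +4.5 | +1.5 | +25.0 |
| 52% | 3 | 89% | +4.9 | −1.1 | +37.0 |
| 77% | 2 | 95% | −1.0 | −5.9 | +17.8 |
| 89% | 2 | 99% | −5.9 | −8.3 | +10.0 |

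C(t) was positive at every timepoint in all of these. The late sign of F(t) depends on how many subjects have already become pain-free.

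**The case against.** The SAP never says that earlier responders go under 'Pain'. A reader might take that as a stated rule, but it is an inference from filling the table with the counts of 11.8.3.2. The shell is in the Data Display Plan, which is not among the documents and may define the cells. This stands, and it limits what can be said about the eventual table. It does not remove the gap. Using the current-pain flag of 10.15.4 would repeat the no-headache-pain table, a single ever-pain-free table would discard timing, and the cumulative reading is written nowhere.

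A reader might also infer that a faster drug will always show zero or negative late differences. Example 2 and the first two rows of the range show otherwise.

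Third, a reader might conclude that the cumulative result by 8 hours is missing, or that this table should answer secondary objective 2, worded "compared with placebo at any timepoint to 8 hours post dose". The documents do not support either. First-at-t categories are mutually exclusive, so a running sum over the same pairs recovers the cumulative difference, and the Kaplan-Meier curve shows cumulative timing by treatment. Objective 2 is put into practice through a separate secondary endpoint, the percentage pain-free at each listed time to 8 hours, analysed in SAP 11.8.2.5. It also carries a no-rescue condition.

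Finally, the endpoint is exploratory, and no test or interval is attached to this difference. That limits the weight of the point. The Kaplan-Meier curve, however, gives no within-subject difference, so it does not replace the paired display.

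**Conclusion.** The point holds as a minor one. SAP 10.16 leaves its cells undefined for first pain-free timepoint. On the plain reading of 11.8.3.2, the paired difference has no fixed direction and can be zero or negative at late times for a faster drug, especially when 24-hour totals are similar. Under the assumed rates above, F(24) ranges from about +5 points (placebo 31% by 24 hours, HR 2) to −10 points (examples 1 and 3), while LAT8881 is never behind cumulatively. The size rests entirely on assumed rates and on the first-at-t filling.

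The protocol's two-way classification has been dropped without being listed in SAP 8.1. The primary analysis, the secondary no-headache-pain analysis and the Kaplan-Meier curve are not affected by the cell definition.

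**What to change.** In SAP 10.16 and 11.8.3.2, define the cells for this endpoint at each t as first pain-free at or before t with no rescue medication before that point, versus not, and compute (b − c)/n on those cells. The no-rescue condition is already part of the exploratory endpoint (Protocol 10.4, SAP 7.4) but is absent from SAP 10.15.5. The same condition should be stated there so that the table and the curve describe the same event.

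Restore the protocol's cross-table of first pain-free timepoint, LAT8881 by placebo, with a row and column for never pain-free. If it is not restored, record the change in SAP 8.1.

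The cost is a few sentences of SAP text and the shell of Table 14.2.6.1. No new data are needed.

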#### 11.8.3.3 Subject Satisfaction Survey

The subject’s satisfaction score for each treatment and preference for LAT8881 or placebo recorded on a 7-point Likert scale will be summarised as a continuous endpoint with mean, SD, median, minimum and maximum. Within-subject difference in the satisfaction score between treatments will also be summarised. Within-subject difference will be compared using paired t-test and p-values will be presented.

If the assumptions for normality are not met using Shapiro-Wilk test, the non-parametric equivalent Wilcoxon signed-rank test will be performed, and unadjusted p-values will be presented.

[REDACTED]

```
proc ttest data = <INDATA>
  paired <TESTVAR1>*<TESTVAR2>;
run;
```

[REDACTED]

[REDACTED]

The subject satisfaction score and preference for each treatment compared to their usual medication for an acute migraine attack will be presented in the same manner. Subjects preferred treatment will be derived as mentioned in section 10.16. The number and percent of subjects preferring LAT8881 60 mg or placebo treatment will be presented.

The difference between the proportions of subjects preferring LAT8881 60 mg compared to placebo will also be presented along with the 95% confidence interval for the difference.

In DDP: Table 14.2.7

Subject satisfaction survey will be listed by subject.

In DDP: Listing 16.2.6.6

#### **11.8.3.4 Association between Change in NRS Pain Score and Baseline Characteristics**

##### Descriptive Summary:

NRS pain scores, NRS symptom scores and most troublesome symptom scores will be summarised by visit and subgroup within treatment.

Descriptive summary of NRS Pain scores, NRS symptom scores and most troublesome symptom scores along with absolute change from baseline results will also be presented by treatment overall and subgroup. Timepoints to be included in this table are: Before IMP was taken (Pre-dose), 30 minutes after IMP taken (t=0.5 hrs), 1 hour after IMP taken (t=1 hr), 1.5 hours after IMP taken (t=1.5 hrs), 2 hours after IMP taken (t=2 hrs), 4 hours after IMP taken (t=4 hrs), 8 hours after IMP taken (t=8 hrs) and 24 hours after IMP taken (t=24 hrs).

The summary will be based on Per-Protocol population.

##### Difference between treatments:

The difference in absolute scores and change from baseline between both treatments will be summarised by timepoint. Timepoints to be included in this table are: Before IMP was taken (Predose), 30 minutes after IMP taken (t=0.5 hrs), 1 hour after IMP taken (t=1 hr), 1.5 hours after IMP taken (t=1.5 hrs), 2 hours after IMP taken (t=2 hrs), 4 hours after IMP taken (t=4 hrs), 8 hours after IMP taken (t=8 hrs) and 24 hours after IMP taken (t=24 hrs). 95% Confidence interval for the difference between treatments will also be provided.

Difference between treatments will be calculated as mentioned in section 10.15.1.

In DDP: Table 14.2.8.1 to Table 14.2.10.3

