Patient satisfaction for each treatment recorded on a 7-point Likert scale and the within-subject difference between treatments will be summarised. The mean difference between treatments will be compared with a paired t-test and the 95% confidence interval for the mean difference will be presented. Additional exploratory analyses to investigate the association between change in headache pain and symptom scores and selected subject baseline characteristics will be undertaken in a similar fashion with descriptive statistics.

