#### 3.3 Exploratory Objectives

- 1. To investigate the percentage of subjects who are “sustained pain-free,” defined as having no headache pain following treatment with oral LAT8881 for a migraine headache compared with placebo, with no use of rescue medication and no relapse of headache pain within 24 hours (24-hour sustained pain-free) after administration*
- 2. To investigate the time to first pain-free timepoint following treatment with oral LAT8881 for a migraine headache compared with placebo to 24 hours post dose, with no use of rescue medication*
- 3. To determine the need for extra analgesic (rescue) medication after treatment with oral LAT8881 administration for a migraine headache, compared with placebo*
- 4. To investigate subject satisfaction with treatment of a migraine headache*
- 5. To investigate other factors influencing the extent of change in pain score and symptom scores in subjects with migraine headaches*

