### 7.4 Exploratory Endpoints

- 1. The percentage of subjects who are "sustained pain-free," defined as having no migraine headache pain at 24 hours, with no use of rescue medication and no relapse of headache pain within 24 hours (24-hour sustained pain-free) after administration*
- 2. The time to first pain-free timepoint following treatment with oral LAT8881 compared with placebo to 24 hours post dose, with no use of rescue medication*
- 3. Supplemental analgesic medication use in the 24 hour post treatment period*
- 4. Subject satisfaction with each treatment based on a 7-point Likert Scale, overall preference for Treatment 1 or Treatment 2, and historical comparison with usual treatment*

5. *Association between change in headache pain and symptom scores and selected subject baseline characteristics, including for example, migraine with/without aura, relationship to menstrual cycle*

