## 8 Statistical Methods

Efficacy endpoints will be summarised in a descriptive manner and analysed using statistical methods described in section 11.8. Changes over time for the primary and secondary efficacy outcomes will be explored using a statistical model as defined in Section 11.8. The level of significance for any statistical tests undertaken will be 0.05 and all tests will be two-sided. Any p-values will be displayed to four decimal places, with p-values less than 0.0001 presented as '<0.0001' and p-values greater than 0.9999 presented as '>0.9999'. All analyses will be done using SAS (version 9.4, SAS Institute Inc., Cary, NC, USA).

Safety endpoints will be summarised in a descriptive manner.

Continuous data will be reported using the following descriptive statistics:

1. Number of observations (n)
2. Mean and standard deviation (SD)
3. Minimum (min) and maximum (max)
4. Median

Minimum and maximum values will be reported to the precision of the endpoint reported with maximum of three decimal places; the mean will be presented with one decimal place more and the standard deviation two decimal places more than the precision of the endpoint reported.

Categorical data will be presented using frequency (n = number of subjects; m = number of events) and percentage (%).

Listings will be provided for all data recorded in the eCRF to study subject profiles. All listings will be sorted by treatment sequence, subject ID, study period and date (if applicable). Unscheduled visit data will only be listed and not included in summaries.

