### 10.15 Analysis Flags

#### 10.15.1 Difference between Treatments

For subjects who took IMP in both visits, difference between their scores at each timepoint will be calculated as below.

Difference at timepoint X = Score (LAT8881 60 mg) at Timepoint X – Score (Placebo) at timepoint X.

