### 10.18 Subgroups for exploratory analysis

Below subgroups will be defined in the analysis datasets and used for the additional exploratory analyses.

- Age at onset: before 15 years and at 15 years or older.

*Age at onset to be calculated as: (Date of episodic migraine diagnosis - Date of birth + 1) / 365.25.*

- Sex group: Male, Female (menstruating), Female (non-menstruating) and Female (postmenopausal)

*For Female subjects, menstruating and non-menstruating will be determined using the start and end dates of the menstrual cycle and the migraine start date. If the migraine start date is between start and end date of menstruation, then the subject will be considered as 'menstruating' and 'non-menstruating' otherwise.*

*Post-menopausal status can be determined by the reasons collected on the diary*

*Any ambiguity in determining the category will be discussed and clarified in the blinded review meeting.*

- Nature of migraine: with aura and without aura.

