#### 11.8.1.3 Mixed Effect Regression Model for repeated measurements (MMRM)

A mixed effects regression model using a covariance pattern will be fitted to the absolute change from baseline in NRS pain scores at each post-IMP timepoint within each treatment period for the PP population.

The model will have fixed effects for treatment period, timepoint, treatment and the interaction between timepoint and treatment. Baseline pain score within each period will be included as a covariate. A random effect for subject will be included to capture the repeated measures nature of the design.

Least squares means and corresponding 95% confidence intervals (CI) will be presented for the mean changes from baseline for LAT8881, Placebo and the difference between LAT8881 vs. placebo at each timepoint. P-values for testing the null hypothesis that the difference in least squares means between LAT8881 and placebo at each timepoint is 0 will be declared statistically significant if the p-value <0.05.

The covariance pattern will take into account the covariance between observations in different treatment periods and the covariance between observations within the same period (i.e. between timepoints).

```
proc mixed data=; class <subject> <study period>  
<treatment> <timepoint>; model <change> = <baseline> <study  
period> <timepoint>|<treatment>; random <subject>  
<subject>*<period>; lsmeans <treatment>|<timepoint> / pdiff;  
run;
```

In DDP: Tables 14.2.1.5

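### Exploratory objective 5 asks whether baseline factors are associated with change in scores, but no planned output gives the difference between subgroups with its uncertainty

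*SAP*

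**What the plan says.** SAP 3.3 sets exploratory objective 5: "To investigate other factors influencing the extent of change in pain score and symptom scores in subjects with migraine headaches". The matching endpoint in SAP 7.4 is "Association between change in headache pain and symptom scores and selected subject baseline characteristics". SAP 10.18 supplies the factors, introduced by "Below subgroups will be defined in the analysis datasets and used for the additional exploratory analyses": age at onset (two levels), sex group (four levels) and nature of migraine (with or without aura).

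SAP 11.8.3.4 then plans three things: descriptive summaries of scores and change from baseline by treatment and subgroup; the difference between treatments at each timepoint, where "95% Confidence interval for the difference between treatments will also be provided"; and plots by treatment and subgroup. The treatment difference is the paired one of SAP 10.15.1: "For subjects who took IMP in both visits, difference between their scores at each timepoint will be calculated as below".

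Protocol 14.5 says that these association analyses "will be undertaken in a similar fashion with descriptive statistics". The only regression model in either document, in SAP 11.8.1.3, has no subgroup term: "The model will have fixed effects for treatment period, timepoint, treatment and the interaction between timepoint and treatment", plus baseline pain score as a covariate and subject as a random effect.

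**The concern.** The objective is a comparison between subgroups: does change in score, or the treatment effect on it, differ by age at onset or aura? The interval in SAP 11.8.3.4 addresses another question, whether LAT8881 differs from placebo. Taken subgroup by subgroup, its reference value of zero means no treatment effect in that subgroup. It does not mean no difference between subgroups.

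Small subgroups make this matter. If the drug worked equally in everyone, one subgroup interval could easily exclude zero while the other did not. Which one did so would depend on subgroup size and chance, with no contribution from the factor. A reader looking for an answer to objective 5 could take that pattern as evidence that the factor influences response.

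**Working it through.** **Inputs from the documents.** 20 planned completers (SAP 4.2); two-sided 0.05 level, hence 95% intervals (SAP 8: "The level of significance for any statistical tests undertaken will be 0.05 and all tests will be two-sided"); seven post-dose timepoints; paired differences only (SAP 10.15.1).

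**Inputs assumed, because the documents give none.** Standardised effect d = true mean paired difference / SD of the paired difference, from 0 to 1.0; subgroup splits from 10/10 to 15/5; SD of the paired difference 2.5 to 3.5 NRS points where a result in points is needed. Over that SD range, d = 0.3 to 1.0 covers true effects from 0.3 × 2.5 = 0.75 to 1.0 × 3.5 = 3.5 points.

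**The plan's own figure.** There is none for the subgroup analysis. The only sample-size figure is 26 enrolled for 20 completers with up to 20% loss: 20 / 0.80 = 25, and 26 × 0.80 = 20.8. The figure of 26 is consistent, so 20 pairs is a fair working number.

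**Step 1: is the interval within subgroup?** The sentence giving the interval does not say so. The section title, the subgroup summaries and plots around it, and the range Table 14.2.8.1 to Table 14.2.10.3 (which fits three outcomes by three factors) all point that way. An unsplit interval would repeat those already planned in SAP 11.8.1.1, 11.8.2.1 and 11.8.2.3.

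**Step 2: discordant intervals when the factor has no influence.** For a subgroup of n pairs, the probability p that its 95% CI excludes zero comes from the noncentral t with n − 1 degrees of freedom and noncentrality d√n. The two subgroups share no subjects, so

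P(exactly one excludes zero) = p1(1 − p2) + p2(1 − p1).

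Examples: d = 0 gives 2 × 0.05 × 0.95 = 9.5%. With d = 0.30 and a 10/10 split, p = 0.136 in each, giving 2 × 0.136 × 0.864 = 23.5%. With d = 0.80 and a 15/5 split, p1 = 0.821 and p2 = 0.281, giving 0.821 × 0.719 + 0.281 × 0.179 = 64.1%.

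| d (same in both subgroups) | 10/10 | 14/6 | 15/5 |
|---|---|---|---|
| 0 | 9.5% | 9.5% | 9.5% |
| 0.30 | 23.5% | 24.0% | 24.2% |
| 0.46 (50% power at n = 20) | 38.2% | 40.3% | 41.4% |
| 0.66 (80% power at n = 20) | 49.7% | 56.1% | 59.5% |
| 0.80 | 47.3% | 58.3% | 64.1% |
| 1.00 | 31.6% | 49.4% | 58.9% |

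**Step 3: the direct contrast.** A two-sample comparison of the paired differences between subgroups flags an uninfluential factor 5% of the time at one timepoint, whatever the common effect (4.7% to 5.4% in 20,000 simulated trials per scenario). If any of the seven timepoints counts, with no adjustment, this rises to 12% to 28% for between-timepoint correlations of 0.9 down to 0.3. The corresponding chance of discordant subgroup intervals at any timepoint is 23% to 48% at d = 0 and 66% to 93% at d = 0.46 (10/10 and 14/6 splits).

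**Step 4: precision of the contrast.** Half-width = t(0.975, 18) × SD × √(1/n1 + 1/n2). For 10/10 and SD 2.5: 2.101 × 2.5 × 0.447 = 2.35 points. For 14/6 and SD 3.5: 2.101 × 3.5 × 0.488 = 3.59 points. For 80% power the subgroup effects must differ by 1.32 SD (10/10) or 1.45 SD (14/6), that is 1.32 × 2.5 = 3.3 points at best and 1.45 × 3.5 = 5.1 points at worst over these inputs.

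**The case against.** The strongest reply is that the plan never draws the inference at issue. The protocol specifies no formal hypotheses and calls this analysis descriptive. SAP 8.4 urges caution over hypothesis tests. SAP 11.8.3.4 contains no test, no p-value and no rule that a factor matters when one interval excludes zero and another does not. Subgroup means, SDs and plots also describe association, and a reader could work out a contrast between two disjoint subgroups from them. This stands. A reader might infer that the SAP makes influence depend on which intervals exclude zero, or offers no other way to see association; the documents support neither.

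Two further inferences also go too far. The within-subgroup reading of the interval is well supported but not stated, and the table layouts are in a Data Display Plan that is not among the documents. A misdirected dose-response programme is speculation too: Protocol 5.3 mentions that follow-on work but does not tie it to aura, age at onset or sex.

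There is also a fair objection to a broad remedy. Contrasts for every factor, timepoint and score would number 5 (one for age, one for aura, three for sex) × 7 timepoints × 5 scores × 2 types = 350, of which 350 × 0.05, or about 17, would exclude zero by chance if nothing differed. A four-level factor crossed with treatment and timepoint has 4 × 2 × 7 = 56 cell means, too many for about 20 subjects.

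The reply does not remove the gap. The descriptive comparison of subgroups carries no stated uncertainty, while the one quantity given an interval is not the quantity that the objective asks about. The caution in SAP 8.4 is general and does not mention subgroups. Leaving changes to the blinded review meeting, as SAP 11.8.3.4 does, makes an amendment easy but specifies nothing.

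**Conclusion.** The point holds as a mismatch between question and output: objective 5 concerns differences between subgroups, and no planned output gives such a difference with its uncertainty. If readers fill the gap by comparing which intervals exclude zero, a two-level factor with no influence looks influential at one timepoint about 9.5% of the time with no drug effect, and roughly 24% to 64% of the time with a common standardised effect of 0.3 to 1.0. A direct contrast would hold this at 5%. The figures rest on 20 pairs, splits of 10/10 to 15/5 and an assumed effect range; none of the effect, SD or split is in the documents.

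The weight is modest. The harm needs a reading that the SAP does not prescribe, the objective is the last of five exploratory ones in a proof-of-concept trial, and no stated decision depends on it. It is a low-cost improvement.

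**What to change.** In SAP 11.8.3.4, for the two-level factors (age at onset, and aura where it is the same for both of a subject's attacks), add the between-subgroup difference with its 95% CI at one timepoint named before unblinding, for:

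- (a) mean change from baseline averaged over both treatments;
- (b) the mean LAT8881-minus-placebo difference in change from baseline.

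Label these exploratory and unadjusted. If all five scores are included, that is 2 factors × 2 contrasts × 5 scores = 20 intervals, of which about one (20 × 0.05) would exclude zero by chance. Keep the within-subgroup summaries and intervals as description, and state that influence is not inferred from one subgroup interval excluding zero while another includes it.

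Keep the four-level sex group descriptive. SAP 10.18 sets menstruating status from the date of the migraine, so a subject's two attacks may fall in different levels and the paired difference then belongs to neither.

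The cost is a few sentences of SAP text and one or two extra table rows, with no new data. The downside is width: about 2.3 to 3.6 NRS points either side for contrast (b) under the SDs and the 10/10 and 14/6 splits above, so most results will be inconclusive.
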